1.2 Primary and Secondary Objectives

The **primary objective** of this study is to evaluate whether a BiCROS fitting improves Speech Intelligibility for speech from the front and noise from the better ear's side compared to no treatment (unaided) for adults with unaidable hearing loss in one ear and aidable hearing loss in the other ear measured with the US Matrix Test.

The **secondary objectives** of this study are:

1. Evaluate whether a BiCROS fitting improves Speech Intelligibility in a setup with speech from the front and noise from the better ear's side compared to the alternative treatment of a monaural hearing aid fitting for adults with unaidable hearing loss in one ear and aidable hearing loss in the other ear measured with the US Matrix Test.
2. Evaluate whether a BiCROS fitting improves Speech Recognition Thresholds (SRT) by 1dB for speech from front in diffuse noise compared to no treatment (unaided) for adults with unaidable hearing loss in one ear and aidable hearing loss in the other ear measured with the US Matrix Test.
3. Evaluate whether a BiCROS fitting improves Speech Intelligibility in diffuse noise compared to the alternative treatment of a monaural hearing aid fitting for adults with unaidable hearing loss in one ear and aidable hearing loss in the other ear measured with the US Matrix Test.
4. Evaluate whether a BiCROS fitting results in improved subjective quality of hearing compared to no treatment (unaided) for adults with unaidable hearing loss in one ear and aidable hearing loss in the other ear measured with a questionnaire (SSQ).
5. Evaluate decrease in subjective listening effort for adults with unaidable hearing loss in one ear and aidable hearing loss in the other ear with a BiCROS fitting compared to no treatment (unaided) with a questionnaire or other means.

2 Design of the clinical investigation

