Visit 3 & Visit 4 (if necessary) Up to 2 hours each	
In-lab Assessments:
 
 • Rating the sound quality of speech and music. • Rating the amount of effort required to listen to speech in noise without the BICROS system and while wearing the BICROS system in different hearing aid settings. • Indicating preference between different hearing aid settings for speech • Repeating speech back in quiet and in noise. • We will ask participants for their opinions of the BICROS hearing aid and document these opinions using a structured process. • Return devices to study audiologist. • Sounds will be delivered by hearing aid, headphone and speakers below uncomfortable levels. • An end of study assessment of hearing levels and ear canal status (audiometry, otoscopy) will be completed.

3 Statistical design and analysis

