3.2.3 Secondary Endpoint Analysis

Whether there is a significant benefit of the BiCROS fitting over the unaided condition in terms of SRTs will be tested using a one-tailed paired samples t-test. The assumption of normally distributed paired differences between unaided and BiCROS will be tested by visually inspecting Q-Q plots, checking skewness and kurtosis against predefined thresholds (skewness < 0.8 and kurtosis < 2) and testing for statistically significant deviations from normality ($p < .05$) using the Shapiro-Wilk-test. Outliers will be defined as differences that lie outside the range between 1.5 times the interquartile range below the first quartile and 1.5 time the interquartile range above the third quartile of the data. Outliers will be removed if they are ≥ 2 standard deviations from the mean. In case of a non-normal distribution, non-parametric testing will take place with a one-sided Wilcoxon rank sum test.

Descriptive analysis with mean and standard deviations will be completed for the questionnaire results. In addition, repeated measures ANOVA with follow-up post hoc t-tests with Bonferroni correction as required will be performed comparing the responses of multiple sub-scales to 0 ("unchanged" - the questionnaire asks participants to rate their experience in terms of change (improvement vs. no improvement for each question) including an option for no change). Factors are conditions (unaided and BiCROS) and SSQ subscales (speech hearing, spatial hearing, and qualities of hearing). Violations of sphericity will be corrected by adjusting the degrees of freedom of the ANOVA using the Greenhouse-Geiser epsilon.

Sound quality ratings and listening effort ratings will be analyzed using repeated measures ANOVA with follow-up post hoc t-tests with Bonferroni correction as required. Factors are conditions (unaided, monaural with omnidirectional and beamformer, and BiCROS with omnidirectional and beamformer) and subscales (clarity, total Impression, and listening effort).

Preference ratings will be analyzed using one-sample Shapiro-Wilk test for normality to detect any significant skew toward a preferred setting, using BiCROS beamformer as the test condition for all comparisons.

According to common standards and Type I error probability of 5% is deemed to be acceptable and the null hypothesis will be rejected if the p -value is equal to or less than 0.05.

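### Listening effort is pooled with clarity and total impression in one ANOVA factor with no scale direction stated, so the condition main effect may partly cancel and in any case does not answer secondary objective 5

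*Combined protocol and SAP*

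**What the plan says.** Section 3.2.3 covers both kinds of rating in one plan: "Sound quality ratings and listening effort ratings will be analyzed using repeated measures ANOVA with follow-up post hoc t-tests with Bonferroni correction as required". It then defines the model: "Factors are conditions (unaided, monaural with omnidirectional and beamformer, and BiCROS with omnidirectional and beamformer") and "subscales (clarity, total Impression, and listening effort"). Condition therefore has five levels and subscale three, and listening effort is one of the three.

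Two other places bear on direction. Secondary objective 5 in section 1.2 is to "Evaluate decrease in subjective listening effort" with BiCROS compared with no treatment, by a questionnaire or some other means. Table 1 in section 2.2.1 describes the task at Visits 3 and 4 as "Rating the amount of effort required to listen to speech in noise". It lists sound quality as a separate task: "Rating the sound quality of speech and music". Section 3.2.1 also lists listening effort ratings separately from subjective rating values.

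The documents give no range, anchors or scoring direction for clarity, total impression or effort. They do not mention reverse scoring or standardising. They do not say whether the main effect, the interaction or a contrast within one subscale decides the question, and post hoc t-tests follow only as required.

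**The concern.** In a condition-by-subscale repeated measures ANOVA, the condition main effect tests differences between condition means after averaging over the subscales. That average describes benefit only if all its components point the same way on comparable ranges. Here one component is a rating for which the stated benefit is a fall, and the other two are qualities for which benefit would naturally be a rise.

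This ANOVA is the only analysis the plan gives for listening effort, a named secondary objective in a study that section 2.1.1 calls confirmatory. Analysed literally, a device that helps equally on all three ratings could give a non-significant condition effect together with a significant interaction. A reader could take that to mean that benefit depends on the subscale, when it reflects only the sign of one scale.

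**Working it through.** **The plan's own figure.** The plan states no sample size or power for the rating ANOVA. The only stated figures are for the primary one-sided paired t-test (section 3.1): 19 for 95% power, 12 for 80%, and 23 with backup. No effect size is given, so 19 cannot be reproduced independently. Solving backwards at one-sided alpha 0.05, 19 and 12 agree with each other for a standardised paired difference of about 0.785 to 0.806. At 0.80, power is 0.956 with 19 and 0.829 with 12. Only n = 19 and n = 23 are carried forward.

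**Inputs from the documents.** Five conditions, three subscales, alpha 0.05 and benefit on effort as a decrease.

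**Assumed inputs.** Higher is better on clarity and total impression; effort is scored as amount of effort; ranges are equal; benefit is equal on all three ratings; within-person error SD is 1.

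**Size of the main effect.** Let d be the benefit of one condition over another on each rating.
- Directions aligned: (d + d + d)/3 = d.
- Effort not reversed: (d + d − d)/3 = d/3.
- Effort not reversed and moving twice as far as the others: (d + d − 2d)/3 = 0. This shows only how much the unstated range matters; nothing in the documents suggests that ratio.

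**Effect relative to noise.** Let ρ be the error correlation among the three ratings of one person in one condition, with all scored toward benefit. The error variance of the average is (1 + 2ρ)/3 when aligned and (3 − 2ρ)/9 when effort is not reversed.
- ρ = 0: d/√0.333 = 1.73d aligned; (d/3)/√0.333 = 0.58d not reversed. Ratio 0.33.
- ρ = 0.5: d/√0.667 = 1.22d aligned; (d/3)/√0.222 = 0.71d not reversed. Ratio 0.58.

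Correlated errors therefore soften the loss but do not remove it.

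**Simulated power of the condition main effect.** Greenhouse-Geisser corrected; largest benefit (BiCROS beamformer versus unaided) 0.8 SD. Profile A sets the five condition effects at 0, 0.5, 0.6, 0.8 and 1.0 of that maximum. Profile B uses 0, 0.25, 0.5, 0.5 and 1.0.

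| Profile, n | ρ | Aligned | Effort not reversed |
|---|---|---|---|
| A, 19 | 0 | 0.94 | 0.15 |
| A, 19 | 0.5 | 0.65 | 0.22 |
| B, 19 | 0 | 0.94 | 0.14 |
| B, 19 | 0.3 | 0.73 | 0.17 |
| B, 19 | 0.6 | 0.58 | 0.24 |
| B, 23 | 0 | 0.98 | 0.19 |
| B, 23 | 0.3 | 0.85 | 0.24 |
| B, 23 | 0.6 | 0.70 | 0.30 |

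**Where the signal goes.** Under profile B with n = 23, power of the condition-by-subscale interaction is 0.87, 0.81 and 0.70 (ρ = 0, 0.3, 0.6) when effort is not reversed. It is about 0.03 when directions are aligned.

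**Contrast within effort.** Reversing effort only changes the sign of BiCROS minus unaided, so a two-sided t-test gives the same p-value. Five conditions give 5 × 4/2 = 10 pairs, so the Bonferroni level is 0.05/10 = 0.005. At n = 23 the simulated power is about 0.33 to 0.38 under either coding; the spread is simulation error.

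**The case against.** The strongest reply is that opposite directions are not established. No anchors are given, objective 5 leaves the instrument open, and the Table 1 wording describes a visit task rather than a scoring rule. An effort item anchored toward effortless, or reversed before analysis, would fit the documents and would not cancel. This stands: the documents make opposite scoring likely, but they do not show it.

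The second reply is that the information is moved, not lost. Opposite coding sends the effect into the interaction, a significant interaction normally leads to follow-ups within each subscale, and those do not depend on coding. This also stands as far as it goes. A reader might infer that every contrast from the model is compromised, or that the Bonferroni follow-ups cannot measure benefit. The documents do not support that: only quantities averaged over subscales are distorted, and section 3.2.3 does not say that follow-ups are averaged. Nor does it say that they will be made within effort, or made whatever the main effect shows, so the reply relies on an analysis the plan has not specified.

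The third reply is that the power figures depend on assumed effects and that the zero-correlation case is the harshest. That is correct, and the table therefore shows a range. Section 1.2 lists no sound quality objective, so objective 5 is the only stated objective clearly touched.

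**Conclusion.** The concern holds in conditional form. Listening effort is a level of the same factor as two sound quality ratings, its benefit is defined as a decrease, and no direction, range or reversal is stated. If effort is scored as amount of effort and the other two as higher-is-better, with equal ranges and equal benefit, the condition main effect shrinks to one third. At a maximum effect of 0.8 SD and n = 19, power then falls from about 0.94 to 0.15 (ρ = 0) or from 0.65 to 0.22 (ρ = 0.5). Effect size, condition profile and correlation are assumptions.

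One part does not depend on coding: a main effect averaged over clarity, total impression and effort does not measure effort, so it cannot answer objective 5 even with directions aligned. That makes this more than a missing scoring detail. It should be corrected, but it concerns a secondary analysis and leaves the primary endpoint and the sample size untouched.

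**What to change.** In section 3.2.3, take listening effort out of the subscales factor and analyse it in its own repeated measures model. State the direction of benefit and prespecify a BiCROS versus unaided contrast as the test of objective 5, naming which BiCROS setting it uses. Keep clarity and total impression in the sound quality ANOVA. State range, anchors and direction for all three ratings.

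If one model is preferred, reverse-score effort to a common range and direction before analysis, and still test objective 5 by the contrast within effort.

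The cost is a few sentences and, for the first option, one more model to report. It needs no new data and no more participants.

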2.1 General

2.1.1 Design Type

This clinical investigation is an interventional study, conducted at one investigation site, with a confirmatory design. The investigation employs a single group of participants that will be tested in all conditions (cross-over) and be blinded towards the intervention condition they are tested in as much as possible (unaided can't be blinded).

Test conditions:

- Experimental intervention: BiCROS fitting: A CROS microphone transmitter is worn on the poorer, unaidable ear and the hearing aid on the better hearing ear.
- Control intervention: Monaural hearing aid fitting: One hearing aid is worn on the better hearing ear.
- Control intervention: BiCROS fitting: A CROS microphone transmitter (with omnidirectional microphone mode) is worn on the poorer, unaidable ear and the hearing aid (with omnidirectional mode) on the better hearing ear.
- Control intervention: Monaural hearing aid fitting: One hearing aid (with omnidirectional mode) is worn on the better hearing ear.
- No intervention: No treatment (unaided), i.e. no CROS transmitter and no hearing aid are worn. (Condition not included in preference ratings because it doesn't allow for quick AB comparisons.)
- The order of conditions will be randomized.

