3.1 Determination of Sample Size

Primary objective

A power analysis was conducted to apply a one-tailed paired samples t-test to compare the difference between the two conditions tested in the primary objective. The required sample size for 95% power with a one-tailed paired t-test is 19.

With additional 4 participants as backup (based on previous research experience), the required number of participants is 23. For 80% power, 12 participants are needed.

Statistical criteria of termination of trial

There are no statistical criteria for stopping the study.

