3.2 Planned Analyses

3.2.1 Datasets to be analyzed, analysis population

Dataset will be the SNRs from the Matrix test across hearing aid conditions, questionnaire responses, subjective rating values, listening effort ratings, and preference ratings.

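### The only planned preference analysis is a normality test, which cannot detect a preference or say which setting is preferred

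*Combined protocol and SAP*

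**What the plan says.** Under Secondary Endpoint Analysis (section 3.2.3) the plan says: "Preference ratings will be analyzed using one-sample Shapiro-Wilk test for normality to detect any significant skew toward a preferred setting". The reference setting is fixed in the same sentence, where the test is to be run "using BiCROS beamformer as the test condition for all comparisons". The decision rule in that section is that "the null hypothesis will be rejected if the p -value is equal to or less than 0.05".

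Preference data are collected and are meant to be analysed. Table 1 in section 2.2.1 lists "Indicating preference between different hearing aid settings for speech" among the in-lab assessments, and section 3.2.1 includes "listening effort ratings, and preference ratings" in the dataset. Section 2.1.1 leaves the unaided state out ("Condition not included in preference ratings") because it does not "allow for quick AB comparisons". The comparisons are therefore between aided settings.

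No section gives the response scale, the value that means no preference, or the number of trials per participant. Nor is any other preference analysis planned. In section 3.2.3 the means and standard deviations are for the questionnaire, and the repeated-measures ANOVAs cover the questionnaire, sound quality and listening effort. Elsewhere in sections 3.2.2 and 3.2.3, Shapiro-Wilk serves only to check an assumption before a t-test or a Wilcoxon test.

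**The concern.** The stated aim is to find out whether ratings lean toward one setting. That is a question about location and direction relative to a neutral point. Shapiro-Wilk has no neutral point and no direction, because it assesses only the shape of the distribution. A rejection could come from coarse categories, a split panel, a ceiling effect or a real preference for either setting. A non-rejection is what one expects when a clear preference happens to be normally distributed on a fine scale.

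Followed as written, the rule could lead the sponsor to report a preference that does not exist, credit the wrong setting, or miss a strong preference. The stakes are limited because preference is not among the objectives in section 1.2. They are not nil: section 1.1 says the study is also meant to support intended claims, and preference is tested at the 5% level.

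**Working it through.** **Inputs.** The test, reference condition and 5% level come from section 3.2.3. Section 3.1 gives the sample sizes: "The required sample size for 95% power with a one-tailed paired t-test is 19", 12 for 80% power, and 19 + 4 = 23 with backups. These were set for the primary objective, and nothing below depends on how they were derived. The plan gives no computed figure for preference, so there is none to reproduce. The rating scales used in steps 2 and 3 are assumptions.

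**Step 1: invariance, which needs no scale.** The statistic is

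W = (Σ aᵢ x₍ᵢ₎)² / Σ (xᵢ − x̄)²,

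where x₍ᵢ₎ are the ordered ratings. The weights sum to zero and are antisymmetric (aᵢ = −aₙ₊₁₋ᵢ).

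- Add c to every rating. The numerator sum gains c·Σaᵢ = 0 and the denominator is unchanged, so W is unchanged.
- Reverse every sign. The order flips, and Σ aᵢ(−x₍ₙ₊₁₋ᵢ₎) = Σ aₙ₊₁₋ᵢ x₍ₙ₊₁₋ᵢ₎, which is the original sum. W is again unchanged.

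Numerically, over 2,000 simulated samples of 19, reversing signs or adding 10 changed the p-value by at most 1.4e-14, which is rounding error.

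**Step 2: rejection rates on assumed scales.** Figures are for n=19, two-sided 5%, with 10,000 runs for Shapiro-Wilk and 3,000 for the signed-rank test.

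| Assumed ratings (0 = no preference) | Shapiro-Wilk | Signed-rank |
|---|---|---|
| Normal, shift 0 | about 5% | about 5% |
| Normal, shift 1 SD | about 5% | 98% |
| Normal, shift 2 SD | about 5% | 100% |
| 7-point (−3 to +3), SD 1.5, mean +1 or −1 | about 45% for each | – |
| 7-point, SD 1.5, mean +2 or −2 | about 95% for each | – |
| 7-point, mean 0, SD 1 to 2 | 25–66% | about 4–6% |
| Half at +2, half at −2, noise SD 1 to 0.5, unrounded | 37–100% | about 4–6% |
| Same, rounded and clipped to 7 points | 84–100% | about 4–6% |
| 100-unit scale, mean 0, SD 15 to 30 | 4–5% | – |

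For 7-point ratings with no net preference, Shapiro-Wilk rejects 14–44% of the time at n=12 and 32–79% at n=23. At n=23 with normal ratings shifted by 0.8 SD, it rejects 5.0% of the time, against 95.8% for a one-sample t-test of zero.

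**Step 3: forced choice, by enumeration at n=19.**

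- A 10-9 split gives Shapiro-Wilk p = 0.000012. The exact binomial p is 1.0.
- A 17-2 split gives Shapiro-Wilk p = 0.00000004. The exact two-sided binomial p is 2 × (1 + 19 + 171) / 2¹⁹ = 382 / 524,288 = 0.0007.
- Every mixed split from 1-18 to 18-1 has Shapiro-Wilk p no larger than 0.000012, so all are rejected.
- A unanimous 19-0 has zero variance, so W is undefined. The strongest possible preference cannot be tested.

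**The case against.** **Skew may mean asymmetry of shape.** On that reading Shapiro-Wilk has some power: it rejects about 88% of the time for a mean-centred exponential at n=23. But it cannot separate skewness from other departures from normality or give its direction. A symmetric distribution centred well away from neutral has no skewness at all.

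**A strong preference on a bounded scale will show up.** This is true, because ratings pile up at one end: about 95% rejection at a mean of +2 on the 7-point scale. The rate at −2 is the same.

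**The scale is unknown, so the rates are hypothetical.** This stands for every rate in the table. On a fine 100-unit scale with no preference, rejection is only 4–5%, so false rejection is not inevitable. Conversely, the statement that a bell-shaped preference goes undetected holds only for fine or continuous scales. The invariance depends on neither.

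**It may be a slip for another test.** The sentence names the test and calls it a test for normality, so this is unlikely. A slip would need the same correction.

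**Preference is not an objective.** This stands, and it limits the weight of the point without making the test answer the question set for it.

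**Conclusion.** The concern holds. The invariance to shift and sign follows from the form of W, for any response scale and sample size at which W can be calculated. Rejection therefore cannot be attributed to preference and gives no direction, and non-rejection does not rule preference out. The size of the error depends on the unstated scale. In the n=19 illustrations, rejection with no net preference ran from 4–5% on a fine scale to every mixed split under forced choice. Rejection with a 2 SD preference was about 5% when ratings were normal. This is a stated rule that is wrong for its purpose, and it should be fixed. It affects the preference results only.

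**What to change.** In section 3.2.3, replace the preference sentence with a rule that:

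1. States the response scale, the value that means no preference, and the number of trials per participant.
2. Reduces each participant's responses to one value per comparison.
3. Tests those values against no preference, for BiCROS beamformer versus each other aided setting compared. Use a one-sample Wilcoxon signed-rank test for ratings, or an exact binomial or sign test for a forced choice.
4. States whether the tests are one- or two-sided (the figures above are two-sided), and reports an estimate with a confidence interval for each comparison.
5. Says how multiplicity is handled. The conditions listed allow up to three comparators (BiCROS omnidirectional, monaural beamformer, monaural omnidirectional). If independent, three tests at 5% carry a family-wise error of 1 − 0.95³ = 14.3%. The section already uses Bonferroni for other post hoc tests.

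Item 2 matters only if trials are repeated, which the plan does not say. Assuming 3 to 6 forced-choice trials each, a within-person correlation of 0.2 to 0.5 and no net preference, pooling all trials into one binomial test at n=19 rejects 7–31% of the time. A sign test on one value per participant rejects 2–3%. It is conservative, which costs some power at this sample size.

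The cost is SAP wording only, with no new data, participants or procedures.
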